OPTIMAL PROTAMINE DOSING FOR HEPARIN REVERSAL FOLLOWING CARDIOPULMONARY BYPASS: A BLINDED RANDOMIZED CONTROL TRIAL COMPARING TWO STRATEGIES

IRB: 20220234

PROTOCOL VERSION 1

MAY 5, 2022

PRINCIPAL INVESTIGATOR: [name]

NCT: NCT05426031

Objectives:

The primary objective is to compare two protamine dosing strategies in cardiac surgical patients. A fixed dosing strategy, using 250 mg of intravenous (IV) protamine, will be compared to a standard dosing strategy of 1mg IV protamine for every 100 IU of heparin given before the initiation of cardiopulmonary bypass (CPB). Only patients with calculated protamine doses over 250 mg will be included. The primary outcome is mean difference in activated clotting time between baseline and reversal of heparin. Secondary outcomes will include additional protamine dosing, chest tube output and units of packed red blood cells transfused.

Additionally, a retrospective review of protamine and heparin dosing will be performed using existing data. This will be done to compare prospective randomized results to our historical practices.

Background:

Currently, protamine dosing for heparin reversal following cardiopulmonary bypass varies highly among centers, and even among practitioners in a given center. Reversal practices include heparin ratio-based dosing, heparin concentration based dosing, and formulaic dosing based on calculations utilizing values like activated clotting time (ACT).¹ These variations in practice seek to address two primary concerns. The first concern is inadequate reversal of heparin following cardiac surgery, leading to bleeding in a patient group at high risk for bleeding and transfusion.² The second concern these variations seek to address is overdosing of protamine, which has also been shown to increase measures of clinical bleeding.³ In the COVID era a third concern has arisen which is drug shortages.

Each of these strategies has advantages and disadvantages. Protamine dosing based on heparin ratios are simple and the most widely employed. There is variation even within this practice since ratios can be based on initial heparin dose or total dose, and heparin dosing itself can be based on ideal or total body weight. The most common form of ratio-based dosing is 1mg protamine to every 100 IU of heparin given before initiation of cardiopulmonary bypass (CPB). Evidence suggests that lower ratios may be just as effective at reversal with no increase in bleeding measures.⁴ While heparin concentration-based dosing objectively determines protamine doses, point-of-care devices for this purpose remain expensive and unavailable in many institutions including ours. Furthermore, the benefit of this strategy remains controversial.¹ Some guidelines support this method with low quality evidence behind the recommendation.

Current guideline recommendations for heparin dosing incorporate low quality evidence to support weight-based dosing.⁵ A commonly cited dose is 300 units/kg of actual body weight. A previous analysis of heparin and protamine dosing strategies have identified an average patient weight of 78 kg, and 91-105 units of heparin per 1 mg of protamine (heparin: protamine ratio), depending on the protamine dosing strategy.⁶ With 300 units/kg and average body weight these ratios would result in an 230-260 mg of protamine doses. Current practices which often employ higher heparin dosing strategies, up to 400 units/kg actual body weight, and 1 mg protamine per 100 units of heparin, often result in much higher protamine doses than this. Some studies supporting low

¹ Hecht, P., Besser, M., & Falter, F. (2020). Are We Able to Dose Protamine Accurately Yet? A Review of the Protamine Conundrum. *The journal of extra-corporeal technology*, 52(1), 63.

² Hajjar L a, Vincent J-L, Galas FRBG, et al. Transfusion requirements after cardiac surgery: the TRACS randomized controlled trial. *JAMA*. 2010;304(14):1559-1567. doi:10.1001/jama.2010.1446.

³ Boer, C., Meesters, M. I., Veerhoek, D., & Vonk, A. B. A. (2018). Anticoagulant and side-effects of protamine in cardiac surgery: a narrative review. *British journal of anaesthesia*, *120*(5), 914-927.

The intent of this investigation is to address the following concerns: the expense of heparin concentration monitoring and controversial evidence supporting its use, variation in practice with ratio dosing strategies, lack of pharmacological support for use of heparin initiation doses for protamine dosing, and lastly, medication shortages. Our hypothesis is that standard heparin dosing, 350 units/kg actual body weight with fixed protamine dosing, 250 mg, will be non-inferior to a conventional ratio-based protamine dosing strategy of 1 mg protamine per 100 units of heparin in patients with calculated protamine doses over 250 mg. We also hypothesize that the fixed dosing group will receive less protamine overall. The outcomes of interest are primarily the pre CPB to post CPB ACT ratio, and secondarily, additional protamine administration and chest tube output.

Inclusion Criteria:

- Patients greater than or equal to 18 years of age undergoing elective cardiac surgery with cardiopulmonary bypass.
- Patients must have a calculated protamine dose greater than 250 mg based on standard 1:1 initial heparin to protamine dosing calculation.

Exclusion Criteria:

- Patients who are under 18 years of age or pregnant.
- Patients undergoing emergency surgery (ASA class E)
- Patients with known coagulation disorders.
- Patients requiring circulatory arrest or deep hypothermia.
- Patients who have not had the appropriate interruption in coumadin, direct oral anticoagulants or nonaspirin antiplatelet agents.
- Patients on pre-operative intravenous unfractionated heparin infusions.
- Patients ineligible for heparin administration due to known adverse reactions including allergy or heparin induced thrombocytopenia or known heparin resistance.
- Patients who are unable to provide informed consent in the form of a signature.
- History of adverse reaction to protamine.
- Have any condition that, in the opinion of the investigator, will compromise the well-being of the patient or the study, or prevent the patient from meeting or performing study requirements.

⁷ Meesters, M. I., Veerhoek, D., de Lange, F., de Vries, J. W., de Jong, J. R., Romijn, J. W., ... & Boer, C. (2016). Effect of high or low protamine dosing on postoperative bleeding following heparin anticoagulation in cardiac surgery. *Thrombosis and haemostasis*, *116*(08), 251-261. ⁸ Tahir R. A review of unfractionated heparin and its monitoring. US pharm. 2007;32(7):26-36.

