- Post-cardiopulmonary bypass ACT
- Patient's weight
- Initial heparin dose
- Total heparin dose
- Initial protamine dose
- Additional protamine dose
- Total Protamine dose
- Time each sample is collected and reported will be recorded
- Packed blood cells units transfused intraoperatively
- Fresh frozen plasma units transfused intraoperatively
- Platelets units transfused intraoperatively
- Cryoprecipitate units transfused intraoperatively
- 4 hour and 24-hour chest tube output

Data collection and release:

Anesthesiologists will administer heparin and protamine in standard fashion. Activated clotting times will be measured by perfusionists in standard fashion. Protamine dose preparation will occur in the UHealth Tower pharmacy for the purposes of blinding and standardization.

Data access will be limited to the listed study investigators only. All investigators will complete required CITI training. Data will be stored on study sheets in individual patient folders locked in anesthesia office with access available to principal investigator only. Original consent forms will be kept in subject study charts, with a copy given to all subjects and a second copy placed in the medical charts. All study charts, regulatory binders will be stored at the Research office located at University of Miami Hospital, [name].The data will be transferred to a password protected University of Miami computer in the department of anesthesia. The excel sheet data will be made available to investigators through password protected excel document.

All study records and documents, will be retained for studies that are subject to both FDA and HIPAA regulations: According to HIPAA regulations will be retained for a minimum of six (6) years following study closure. Our research department will retain all research data until the later of any of these possible dates listed above.

Data Management:

Total number of subjects: 130

Using retrospective sample data and STATA v 17.0 and considering a power = 0.80 and alpha = 0.05 and equal randomization to control and experimental groups, and 1 pre and 1 post intervention (protamine) measurement the sample sizes required to be able to detect a 2-sided difference between groups of 5, 10, or 15 were as follows¹¹:

DD power calc: n=	= 230	mde= 5	power=.8	p=.5	pre=1	post=1	depvar=act
DD power calc: n=	= 59	mde=10	power=.8	p=.5	pre=1	post=1	depvar=act

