DD power calc: n=	= 27	mde=15	power=.8	p=.5	pre=1	post=1	depvar=act

Previous studies comparing ACT devices have used a difference of 10 seconds as clinically meaningful.¹² To detect a difference of 10, we would need to be powered to 118 subjects. We have chosen 130 subjects to account for any patients with incomplete data or that need excluded after enrolment for any reason.

Risks to subjects:

This study poses minimal risk to patients. Additional heparin will be administered to ensure an ACT > 450 seconds prior to initiation of CPB. Additional protamine will be administered after the initial post CPB dose if the ACT values are greater than 20% of baseline, or if there is concern for clinical bleeding.

Potential Benefits

Direct potential benefits cannot be guaranteed to the patients. This is a study that seeks to compare a type of protamine dosing strategy and increase the knowledge of heparin reversal in cardiac bypass surgery.

¹¹ Burlig F, Preonas L, Woerman M. Panel data and experimental design. Journal of Development Economics. 2020 May 1;144:102458.

¹² Li H, Serrick C, Rao V, Yip PM. A comparative analysis of four activated clotting time measurement devices in cardiac surgery with cardiopulmonary bypass. Perfusion. 2021 Sep;36(6):610-9.

Vulnerable Populations:

This study will not include any vulnerable patient population. Pregnant women, prisoners and patients unable to provide consent in the form of a signature will be excluded

Setting:

Research consents will be obtained in the operating room holding area of University of Miami Hospital for patients admitted the day of surgery. In hospital patients will be consented the night prior to surgery in their admitted locations. Heparin and protamine administration, and ACT measurements will take place within the Operating Room, as is standard. Post-surgical care and monitoring including blood product administration and chest tube output recording will be conducted in the intensive care unit

Resources available:

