The Principal investigator (and/or Study Team members) will record (e.g. write down, abstract) the data collected in a manner that does not include any direct identifiers (see list in the instructions for Section 15 of this protocol) of any subject. Instead, the Principal Investigator and/or Study Team members shall will assign a code (that is not derived in whole or in part from any direct or indirect identifiers of the individual) to each study subject and link the code to the study subject's identity. The link to each subject's identity and/ or other identifiable information will be maintained on a document separate from the research data.

Biospecimens

Not applicable. No biospecimens will be collected

Bio-Specimens obtained for this research will be stored without any direct or indirect identifiers.

Bio-Specimens obtained for this research will be stored in a de-identified coded manner.

When required to transport data or bio-specimens for this research, the research team will transport the data and bio-specimens in a de-identified (or anonymous) manner with a link to the individual subject's identity maintain separately from the data and/or bio-specimen.

Authorization for Use and Disclosure of Protected Health Information (HIPAA)

Type of Request:

Waiver of Authorization for access to medical record for subject identification/recruitment. Waiver of Authorization for access to medical record to obtain data for the research.

Confirm that you will destroy or de-identify the information you collect at the earliest opportunity. \Box *I confirm*

Confirm that the information you collect will not be reused or disclosed to any other person or entity, except as required by law, for authorized oversight of the research study or for other research for which the use or disclosure of PHI is permissible.

I confirm

Provision to Protect Privacy Interests of Subjects:

Study information packets and consent forms (attached) provided to each patient will list all investigators and will provide immediate contact information for the principal investigator. Subjects will be advised that the can withdrawal from the study at any time point. If subjects withdrawal all information regarding that subjected will be deleted and subject files will be placed in approved medical record disposal bins.

Consent Process:

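### The hypothesis is non-inferiority, but the only statistical framework is a sample size for a two-sided difference, with no margin, confidence-limit rule or success criterion

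*Combined protocol and SAP*

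**What the plan says.** Three parts of the protocol bear on this, and they do not describe the same question.

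- **Background, last paragraph.** The hypothesis is that "fixed protamine dosing, 250 mg, will be non-inferior to a conventional ratio-based protamine dosing strategy". The same paragraph names a ratio of ACT before and after bypass as the main outcome.
- **Objectives.** "The primary objective is to compare two protamine dosing strategies in cardiac surgical patients". Non-inferiority is not mentioned. The primary outcome here, and again under Study End Point, is a mean difference in ACT and not a ratio.
- **Data Management.** With power 0.80, alpha 0.05 and "equal randomization to control and experimental groups", the sample size is the number needed to "detect a 2-sided difference between groups of 5, 10, or 15". The printed rows are n = 230, 59 and 27. The choice among them rests on this sentence: "Previous studies comparing ACT devices have used a difference of 10 seconds as clinically meaningful". Then: "To detect a difference of 10, we would need to be powered to 118 subjects". Enrolment is raised to 130 to allow for incomplete data and later exclusions.

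No section names a primary test, a margin, a confidence-limit rule or a result that would confirm the hypothesis.

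**The concern.** A test for a difference and a test for non-inferiority answer different questions. Failing to find a difference shows that the data are compatible with none. It does not show that a loss of reversal larger than some tolerable amount has been excluded. As written, a reader cannot tell which result would confirm the hypothesis.

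The 10 s figure is the nearest thing to a margin, but the protocol uses it as a difference to detect and takes it from comparisons of measuring devices. It is not called a margin, tied to a confidence limit, or argued for as an acceptable loss of heparin reversal. It also has no meaning on the ratio scale of the Background paragraph.

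At stake is the trial's headline claim. If a margin is chosen after the data are seen, it can be fitted to the result.

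**Working it through.** **Inputs.** From Data Management: two-sided alpha 0.05, power 0.80, 1:1 allocation, one measurement before and one after protamine; n = 230, 59, 27 for differences of 5, 10, 15; 118 needed, 130 enrolled. The SD is not stated, so 118 cannot be reproduced from stated inputs. What can be checked is whether the three rows agree with one another, and which SD they imply. I assume a two-sample t-test on the ACT change (post minus baseline, fixed minus standard).

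**Step 1: implied SD.** In the normal approximation, SD = Δ × √(n/2) / (1.960 + 0.842), with n per arm. For the 10 s row this is 10 × √29.5 / 2.802 = 19.4 s. Solving with the noncentral t:

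| Row (n, Δ) | SD if n is per arm | SD if n is a total |
|---|---|---|
| 230, 5 s | 19.10 | 13.48 |
| 59, 10 s | 19.23 | 13.48 |
| 27, 15 s | 19.31 | 13.37 |

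The rows are consistent under either reading. The protocol's step from 59 to 118 (2 × 59) supports per arm, and 59 and 27 do not split equally as totals. Per arm is therefore the main case below. SD 19.23 is used; with 19.1 the results move by about half a percentage point.

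**Step 2: where the two decision rules part (SD 19.23).** Standard error = SD × √(4/N).

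- N=118: 19.23 × √(4/118) = 3.54 s; half-width of the 95% CI = 1.981 × 3.54 = 7.01 s.
- N=130: 3.37 s; half-width 1.979 × 3.37 = 6.67 s.

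A prolongation is non-significant if it is below the half-width. It meets a 10 s confidence-limit rule only if it is below 10 minus the half-width, which is 2.99 s (3.33 s at 130). Observed prolongations of about 3.0 to 7.0 s (3.3 to 6.7 s) are thus non-significant yet fail the rule.

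**Step 3: how often (SD 19.23; N=118, with N=130 in brackets).**

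- True prolongation 10 s: noncentrality 10/3.54 = 2.82 (2.96), and P(non-significant) = 0.200 (0.163). Under the 10 s rule, a false claim at that point has probability 0.025 by construction.
- Non-significant yet failing the 10 s rule (simulation): 17.5% (13.8%) of trials at true 0, and 42% (37%) at true 5 s.

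**Step 4: the other reading (SD 13.48).** The standard error is 2.48 (2.36) s and the half-width 4.9 (4.7) s. P(non-significant | true 10 s) = 0.021 (0.013). The rules still disagree, in two directions. At a true 5 s:

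- non-significant yet failing the rule: 2.8% (0.7%) of trials. At N=118, 48% of trials are non-significant, so about 6% of those results fail the rule.
- fixed dosing significantly worse yet meeting the rule: 5.8% (11.7%) of trials.

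**Step 5: power of the confidence-limit rule at the planned size.** Noncentrality is (margin − true difference) / standard error.

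| Margin, true difference | SD 19.23: N=118 / 130 | SD 13.48: N=118 / 130 |
|---|---|---|
| 10 s, 0 | 80% / 84% | 98% / 99% |
| 10 s, 2.5 s | 56% / 60% | 85% / 88% |
| 5 s, 0 | 29% / 31% | 52% / 56% |

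The first row matches the protocol's own power because a 10 s margin with no true difference is the same distance as a 10 s difference tested against zero.

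**The case against.** The strongest reply is that the harm is conditional. The protocol nowhere says that a non-significant result will be read as non-inferiority; it names no primary test, and its objective is only to compare. A reader might infer from the two-sided sample size that this misreading is planned. The documents do not support that, so the 20% describes what would follow from one possible reading and is not an error rate built into the plan. This stands as a limit on the size of the point. It does not remove the gap, since the hypothesis is stated and nothing says how to judge it.

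A second reply is that the magnitude rests on an SD the protocol does not give. That also stands. The per-arm reading is better supported, but only the retrospective data can settle it. A smaller SD does not make a rule unnecessary: at 13.5 s the disagreement shifts partly to results that are significantly worse yet within 10 s.

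Two stronger readings are tempting and should be resisted. One is that the design cannot test non-inferiority. It can, because the planned data yield a confidence interval that can be set against a margin. The other is that the trial is too small. With a justified 10 s margin and no true difference, it is not.

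Finally, it could be said that 10 s is already the margin in all but name. The text does not bear this out, for the reasons given above. Post-enrolment exclusions and the deletion of withdrawn subjects' data are separate matters and are not needed for this point.

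**Conclusion.** The point holds and should be fixed before unblinding. The stated hypothesis is non-inferiority, the only framework is for a two-sided difference, and following the plan as written cannot support its main claim.

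If non-significance were taken as non-inferiority, a true 10 s prolongation would pass in about 20% of trials at 118 (16% at 130), against 2.5% under a 10 s limit rule. If the printed n were a total, this would be about 2% (1%), with some disagreement between the rules remaining. These figures assume a back-solved SD, a t-test on ACT change with 1:1 allocation, and 10 s used as an illustrative margin. The absence of a margin and rule does not depend on any of them; it is judged on the text supplied, which lacks a short stretch after Resources available.

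**What to change.** Choose one route before unblinding.

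**Route 1, if non-inferiority is the aim.**

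- Use one primary scale: the mean difference in ACT change (post minus baseline, fixed minus standard), as in Objectives and Study End Point. Reconcile the ratio wording in Background to it.
- State a margin and justify it as an acceptable loss of reversal. The protocol's 10 s is the candidate, but device comparisons alone do not justify it.
- Declare non-inferiority only if the upper limit of the two-sided 95% CI is below the margin, and say that a non-significant difference will not be read as non-inferiority.
- Say how a result that is significantly worse but within the margin will be reported.
- State the SD from the retrospective data, whether the printed n is per arm, and the power for this rule.

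*Cost:* a wording amendment, with no extra patients if 10 s is justified and the true difference is 0. The sponsor is then bound by the margin. If the true difference is 2.5 s, power is 56–60% at SD about 19 s, and 80% would need about 210 evaluable patients (104 at SD 13.5 s). If only a 5 s margin can be justified, 80% power at true 0 would need about 468 (232).

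**Route 2, if non-inferiority is not the aim.** Reword the hypothesis as a two-sided comparison, report the difference with its 95% CI, and make no non-inferiority claim.

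*Cost:* wording only, but the trial gives up the claim it now sets out to make.

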- Post-cardiopulmonary bypass ACT
- Patient's weight
- Initial heparin dose
- Total heparin dose
- Initial protamine dose
- Additional protamine dose
- Total Protamine dose
- Time each sample is collected and reported will be recorded
- Packed blood cells units transfused intraoperatively
- Fresh frozen plasma units transfused intraoperatively
- Platelets units transfused intraoperatively
- Cryoprecipitate units transfused intraoperatively
- 4 hour and 24-hour chest tube output

Data collection and release:

Anesthesiologists will administer heparin and protamine in standard fashion. Activated clotting times will be measured by perfusionists in standard fashion. Protamine dose preparation will occur in the UHealth Tower pharmacy for the purposes of blinding and standardization.

Data access will be limited to the listed study investigators only. All investigators will complete required CITI training. Data will be stored on study sheets in individual patient folders locked in anesthesia office with access available to principal investigator only. Original consent forms will be kept in subject study charts, with a copy given to all subjects and a second copy placed in the medical charts. All study charts, regulatory binders will be stored at the Research office located at University of Miami Hospital, [name].The data will be transferred to a password protected University of Miami computer in the department of anesthesia. The excel sheet data will be made available to investigators through password protected excel document.

All study records and documents, will be retained for studies that are subject to both FDA and HIPAA regulations: According to HIPAA regulations will be retained for a minimum of six (6) years following study closure. Our research department will retain all research data until the later of any of these possible dates listed above.

Data Management:

Total number of subjects: 130

Using retrospective sample data and STATA v 17.0 and considering a power = 0.80 and alpha = 0.05 and equal randomization to control and experimental groups, and 1 pre and 1 post intervention (protamine) measurement the sample sizes required to be able to detect a 2-sided difference between groups of 5, 10, or 15 were as follows¹¹:

DD power calc: n=	= 230	mde= 5	power=.8	p=.5	pre=1	post=1	depvar=act
DD power calc: n=	= 59	mde=10	power=.8	p=.5	pre=1	post=1	depvar=act
DD power calc: n=	= 27	mde=15	power=.8	p=.5	pre=1	post=1	depvar=act

Previous studies comparing ACT devices have used a difference of 10 seconds as clinically meaningful.¹² To detect a difference of 10, we would need to be powered to 118 subjects. We have chosen 130 subjects to account for any patients with incomplete data or that need excluded after enrolment for any reason.

Risks to subjects:

This study poses minimal risk to patients. Additional heparin will be administered to ensure an ACT > 450 seconds prior to initiation of CPB. Additional protamine will be administered after the initial post CPB dose if the ACT values are greater than 20% of baseline, or if there is concern for clinical bleeding.

Potential Benefits

Direct potential benefits cannot be guaranteed to the patients. This is a study that seeks to compare a type of protamine dosing strategy and increase the knowledge of heparin reversal in cardiac bypass surgery.

¹¹ Burlig F, Preonas L, Woerman M. Panel data and experimental design. Journal of Development Economics. 2020 May 1;144:102458.

¹² Li H, Serrick C, Rao V, Yip PM. A comparative analysis of four activated clotting time measurement devices in cardiac surgery with cardiopulmonary bypass. Perfusion. 2021 Sep;36(6):610-9.

Vulnerable Populations:

This study will not include any vulnerable patient population. Pregnant women, prisoners and patients unable to provide consent in the form of a signature will be excluded

Setting:

Research consents will be obtained in the operating room holding area of University of Miami Hospital for patients admitted the day of surgery. In hospital patients will be consented the night prior to surgery in their admitted locations. Heparin and protamine administration, and ACT measurements will take place within the Operating Room, as is standard. Post-surgical care and monitoring including blood product administration and chest tube output recording will be conducted in the intensive care unit

Resources available:

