Potential subjects will be identified using the daily released operating room schedule. Patients on the schedule will be pre-screened using available medical data for exclusion criteria. If patients do not meet any of the exclusion criteria they will be visited by the Principal Investigator, Sub-investigator and/or Study coordinators on the morning of surgery or the night before depending on their admission status. If the subject is currently an inpatient at the hospital, the medical team taking care of the patient will be approached by the study team to get permission to approach the subject. Study details, risks, benefits and alternatives will be discussed with each potential subject. If the patient shows interest into the study, the PI will notify research personnel of potential participant to start the process of consent. Study information and informed consent document (attached) will be provided to each subject. If the patient agrees to the study a copy of the signed consent will be provided to the patient and one placed in the patient medical chart. The original document will be placed in the study specific subject folder.

Study End Point:

Primary Outcome: Mean difference in activated clotting time

Primary Outcome Measure Description: Activated clotting time is going to be measured with the Hemocron Elite device (point of care).

Primary Outcome Measure Timeframe: two time points: once before incision and five minutes after protamine administration.

Secondary outcome: additional protamine dosing Secondary outcome Measure Description: measured in mg. Secondary outcome Measure Timeframe: the additional amount of protamine used on the patient will be added and recorded at the end of surgery.

Secondary outcome: chest tube output Secondary outcome Measure Description: measured in mL Secondary outcome Measure Timeframe: measured since the beginning of surgery for 24 hours

Secondary outcome: units of red blood cells transfused Secondary outcome Measure Description: measured in units Secondary outcome Measure Timeframe: measured only during the time of surgery.

Confidentiality:

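### No primary analysis model is stated; the sizing points to an unadjusted change in ACT, and adjusting for the baseline ACT would be at least as precise in large samples

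*Combined protocol and SAP*

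**What the plan says.** The primary outcome is described in three places.

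- Objectives: the "mean difference in activated clotting time between baseline and reversal of heparin".
- Study End Point: "Primary Outcome: Mean difference in activated clotting time", taken at "two time points: once before incision and five minutes after protamine administration".
- The hypothesis paragraph at the end of Background: "The outcomes of interest are primarily the pre CPB to post CPB ACT ratio".

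The sample size in Data Management was obtained "Using retrospective sample data and STATA v 17.0", "considering a power = 0.80 and alpha = 0.05 and equal randomization to control and experimental groups", with "1 pre and 1 post intervention (protamine) measurement". The printed lines are labelled DD, presumably difference-in-differences, with pre=1, post=1 and ACT as the dependent variable. They give n of 230, 59 and 27 for differences of 5, 10 and 15. The text continues: "To detect a difference of 10, we would need to be powered to 118 subjects". The plan enrols 130.

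The available text names no test, regression model or covariate for the primary outcome. Baseline adjustment is not mentioned, although pre- and post-bypass ACT are both on the list of stored data.

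**The concern.** With no model written down, at least three analyses remain open until the data are seen: the difference in change, the pre-to-post ratio, and a baseline-adjusted comparison. They can give different estimates and intervals from the same data.

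The outcome definition and the one-pre, one-post sizing together suggest the raw change score. Subtracting baseline assumes that each extra second of baseline ACT carries through in full to the post-protamine ACT. If the true slope is below 1, subtraction adds baseline noise to the comparison. The trial may then give away precision that its own measurements already provide.

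**Working it through.** **Inputs from the documents.** Two-sided alpha 0.05, power 0.80, 1:1 allocation, target difference 10 s, printed n of 230, 59 and 27 for 5, 10 and 15 s (all in Data Management). Neither the SD of ACT nor the pre-post correlation is given.

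**Step 1: what the printed n imply.** For a two-arm comparison of change scores, n per arm = 2 × (SD of change × 2.802 / difference)², where 2.802 = 1.960 + 0.842. Solved for the SD:

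| Difference (s) | Printed n | SD of change if n is per arm | SD of change if n is total |
|---|---|---|---|
| 5 | 230 | 19.1 s | 13.5 s |
| 10 | 59 | 19.4 s | 13.7 s |
| 15 | 27 | 19.7 s | 13.9 s |

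With t quantiles, one SD of 19.1 s read per arm returns 231, 59 and 27. The three lines therefore fit a single two-sided comparison of changes. This is calibration: without the SD, the plan's figure cannot be reproduced independently. The text doubles 59 to 118, which is the per-arm reading.

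**Step 2: precision of the two analyses.** Let r be the pre-post correlation and k = post SD / pre SD.

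- Variance of change: SDpre² + SDpost² − 2r·SDpre·SDpost
- Residual variance after baseline adjustment: SDpost²(1 − r²)
- Change minus adjusted: (SDpre − r·SDpost)², which cannot be negative and is zero only when r·k = 1
- Ratio, adjusted to change: k²(1 − r²) / (1 + k² − 2rk)

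Example with k = 1, r = 0.4: (1 − 0.16) / (2 − 0.8) = 0.84 / 1.2 = 0.70.

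**Step 3: effect on the trial.** Take 59 per arm and an SD of change of 19.2 s, the value at which noncentral-t power for 10 s is 80%. The change-score 95% half-width is 1.96 × 19.2 × √(2/59) = 6.9 s. The adjusted half-width is that figure times the square root of the variance ratio. All values of r and k are assumed.

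| k | r | Variance ratio | Power for 10 s | 95% half-width (s) |
|---|---|---|---|---|
| change score | – | 1 | 80% | 6.9 |
| 1 | 0.2 | 0.60 | 95% | 5.4 |
| 1 | 0.4 | 0.70 | 92% | 5.8 |
| 1 | 0.6 | 0.80 | 88% | 6.2 |
| 1 | 0.9 | 0.95 | 82% | 6.8 |
| 1.5 | 0.2 | 0.815 | 87% | 6.3 |
| 1.5 | 0.4 | 0.922 | 83% | 6.7 |
| 1.5 | 0.6 | 0.993 | 80% | 6.9 |
| 2 | 0.2 | 0.914 | 83% | 6.6 |
| 2 | 0.4 | 0.988 | 81% | 6.9 |
| 2 | 0.6 | 0.985 | 81% | 6.9 |
| 1.25 | 0.8 | 1.00 | 80% | 6.9 |

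If 59 were a total (SD about 13.5 s), change-score power with 59 per arm is already 98%. Adjustment then mainly narrows the interval, from 4.9 s to between 3.8 and 4.7 s at k = 1.

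**Step 4: finite-sample check.** Simulating 10,000 trials per setting at 59 per arm gave adjusted power of 0.950, 0.916, 0.879 and 0.813 at k = 1 (r = 0.2, 0.4, 0.6, 0.9), with type I error between 0.046 and 0.053. In a tie case (k = 1.5, r = 2/3), power was 0.797 adjusted against 0.803 for change, and the variance ratio was 1.006. A separate simulation of another tie case (k = 2, r = 0.5) gave 1.008. The cost when adjustment cannot help is about 1% of variance.

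**The case against.** The strongest reply is that nothing in the documents shows precision is actually lost. A change score is unbiased under randomisation, the gain rests on assumed values, and at k = 2 it is 9%, 1% and 2% of variance at r = 0.2, 0.4 and 0.6. This stands as a limit on size. It does not alter the ordering, because adjustment cannot do worse in large samples and costs almost nothing at this sample size.

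The power figures use 59 per arm, but 130 are planned. With all 65 per arm evaluable and an SD of 19.2 s, change-score power is about 84%. That is correct, but the variance ratios do not change.

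The hypothesis is one of non-inferiority and no margin is stated, so an adjusted difference with an interval would still lack a decision rule. That is true, but it is a separate gap that exists whichever model is chosen. It also means the power figures here describe only the two-sided 10 s comparison in Data Management.

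The stored item is called only a pre-bypass ACT, while Procedures also describes an ACT checked after heparin and before bypass. This stands, and the covariate must be tied to the pre-incision reading.

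**Conclusion.** The point holds. No primary model is stated. An unadjusted change comparison is the fair reading of the outcome definition and the sizing, though it remains an inference, and the ratio in the hypothesis paragraph contradicts it. Baseline adjustment is at least as precise in large samples and estimates the same between-arm difference, provided the outcome stays on the difference scale.

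The gain runs from none (r·k = 1) to a 40% reduction in variance at k = 1, r = 0.2, the most favourable case tabulated. On the per-arm reading of 59, that is between no gain in power and a rise from 80% to 95%. Its true size cannot be fixed from the documents. This is a gap in prespecification and an available improvement in efficiency. It is not an error in the stated sample size, and a change-score analysis would not be invalid.

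**What to change.** 1. Settle the outcome scale. The difference in seconds is the one the sample size uses, so the ratio in the hypothesis paragraph should be reconciled with it.
2. State the primary analysis as a linear model of the ACT five minutes after protamine on treatment arm, adjusted for the pre-incision ACT. Report the adjusted mean difference with its 95% confidence interval, and the raw mean change in each arm as descriptive.
3. In the stored-data list, identify the baseline item as the pre-incision reading.
4. Report the pre-post correlation and both SDs from the retrospective data behind the sample size, after confirming that those data use the same two time points. The size of the gain is then known before enrolment.

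The cost is one decision on scale, a few sentences of text, three summary figures from data the sponsor already holds, and one degree of freedom. No new measurements and no extra patients are needed.
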